### 6.2.1. Baseline

Unless noted otherwise for a particular assessment, results obtained just prior to the start of study treatment on Day 1 of Cycle 1 will serve as the baseline values. If not available, the most recent screening results prior to the start of study treatment on Day 1 of Cycle 1 will be considered the baseline values. Transfusions history includes the type, number of units, reason, and date of transfusions for the 8 weeks prior to the start of study treatment on Day 1 of Cycle 1. EORTC QLQ-30 and EQ-5D are to be completed prior to the start of study treatment on Day 1 of Cycle 1 and prior to interaction with study personnel.

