### 5. TABLE OF EVENTS

**Table 3: Table of Events**

Events	Screening Phase	Treatment Phase a							Follow-up Phase a	
	Screening	28-day cycles							EOT b	Follow-up
		Cycles 1 to 2				Cycles 3 to 4		Cycle 5 and beyond		
	Days -28 to -1	Day 1	Day 8	Day 15	Day 22	Day 1	Day 15	Day 1		
Informed Consent	x c									
IVRS Registration and Calls	x	x d				x		x	x	
Inclusion & Exclusion Criteria	x	x e, f								
Demographics	x									
Initial AML Diagnosis	x									
Prior AML Therapies	x									
AML Disease Status	x g									
Central Testing of IDH2 Gene Mutations on BMA and PB	x g									
Medical History	x									
Prior Medications and Procedures	x h									
Eligibility of CCR Options	x i									
EORTC QLQ-C30 and EQ-ED-5L		x				x		x	x	
ECOG Performance Status	x	x				x		x	x	
Physical Exam j	x	x				x		x	x	
Vital Signs	x	x	x	x	x	x	x	x	x	

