d The subject should start study treatment (ie, Day 1 of Cycle 1) within 3 days after randomization.

e Subject should continue to be eligible for study entry prior to the start of study treatment on Day 1 of Cycle 1.

- f Cycle 1 only.
- g See Section 6.1 for details regarding collecting BMA, BMB, PBS and cytogenetics at screening for assessing AML disease status, collecting BMA and PB at screening for central testing IDH gene mutations [REDACTED]. In the event that the central laboratory result is delayed and precludes acute clinical management of a subject who has confirmed IDH2 gene mutation by local evaluation, the subject may be eligible for randomization with approval by the Medical Monitor.
- h All prior medications (prescription and non-prescription) taken and treatment procedures received from the 4-week period (ie, 28 days) prior to starting study treatment (including those prior to the start of study treatment on Day 1 of Cycle 1), and all prior anticancer therapies, regardless of discontinuation date of treatment.
- i Documentation of CCR treatment option selected by the investigator must occur prior to randomization.
- j Source documented only.
- k The BSA calculation is per the Dubois & Dubois formula:  $BSA (m^2) = \text{weight (kg)}^{0.425} \times \text{height (cm)}^{0.725} / 139.2$ . Where applicable, the dose should be calculated on Day 1 of each treatment cycle.
- l These assessments will be done locally.
- m The screening ECHO does not need to be repeated if a prior ECHO or multi-gated acquisition (MUGA) scan has been performed within 28 days prior to the start of study treatment.
- n Pregnancy test is required for all FCBPs (see Section 4.2 for the definition). Serum  $\beta$ -hCG pregnancy test (sensitivity of at least 25 mIU/mL) will be performed centrally at screening. For FCBP subjects, a local serum or urine (investigator's discretion under local regulations)  $\beta$ -hCG pregnancy test (sensitivity of at least 25 mIU/mL) is to be done within 72 hours prior to study treatment administration on Day 1 of every treatment cycle in the Treatment Phase and at the EOT visit. Negative results are required for study treatment administration.

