## 6.9. Quality-of-Life

Two instruments, the European Organization for Research and Treatment of Cancer Quality-of-Life questionnaire (EORTC QLQ-C30) and EuroQoL Group EQ-5D, will be used for HRQoL.

The EORTC QLQ-30 ([Aronson, 1993](#)) is a validated quality of life measure applicable to subjects with any cancer diagnosis. It is composed of 30 items that address general physical symptoms, physical functioning, fatigue and malaise, and social and emotional functioning. Subscale scores are transformed to a 0 to 100 scale, with higher scores on functional scales indicating better function and higher scores on symptom scales indicating worse symptoms. The EORTC QLQ-C30 is available in many languages. This instrument takes 10 to 15 minutes to administer. The EORTC QLQ-C30 data will be captured using a portable electronic tablet computer. See [Appendix I](#) for an example.

The EQ-5D is a standardized instrument for use as a measure of health outcome. It provides a simple descriptive profile and a single index value for health status, and is applicable to a wide range of health conditions and treatments. The EQ-5D is available in many languages and it takes approximately 5 minutes to complete. EQ-5D data will be captured using a portable electronic tablet computer. See [Appendix J](#) for an example.

It is important that every subject completes all assessments of EORTC QLQ-30 and EQ-5D at every specified time point, prior to dosing and prior to interaction with study personnel, to minimize the amount of missing data.

[Redacted]

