### **7.4. Packaging and Labeling**

This is an open-label study. The label(s) for IP will include Sponsor name, address and telephone number, the protocol number, IP name, dosage form and strength (where applicable), amount of IP per container, lot number, expiry date (where applicable), medication identification/kit number, dosing instructions, storage conditions, and required caution statements and/or regulatory statements as applicable. Additional information may be included on the label as applicable per local regulations.

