### **12.2. Emergency Identification of Investigational Products**

This is an open-label study; therefore, IP will be identified on the package labeling.

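### The HRQoL baseline may be taken up to 3 days after open-label randomization, and the SAP's general baseline rule would treat BSC-only subjects differently

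*Protocol*

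**What the plan says.** The effect of AG-221 on HRQoL compared with CCRs is a stated secondary objective, measured with the EORTC QLQ-C30 and the EQ-5D-5L.

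- **First completion.** Protocol Section 6.2.1: "EORTC QLQ-30 and EQ-5D are to be completed prior to the start of study treatment on Day 1 of Cycle 1". In Table 3 the row "EORTC QLQ-C30 and EQ-ED-5L" has no screening entry. It is marked at Day 1 of each cycle and at EOT. The screening list in Section 6.1 names neither instrument, and the SAP copy of the table (Section 15.4) shows the same row.
- **Order of events.** Table 3, footnote d: "The subject should start study treatment (ie, Day 1 of Cycle 1) within 3 days after randomization".
- **Blinding.** Section 12.2: "This is an open-label study; therefore, IP will be identified on the package labeling".
- **Conditions on completion.** Section 6.9 asks for completion "prior to dosing and prior to interaction with study personnel, to minimize the amount of missing data"; Section 6.2.1 repeats the condition on staff contact. Neither mentions randomization or disclosure of the arm.
- **Fallback.** Section 6.2.1 adds a general rule for baseline values: "If not available, the most recent screening results prior to the start of study treatment on Day 1 of Cycle 1" serve instead.
- **SAP baseline.** Section 5.1 uses the last value up to the start of treatment on Cycle 1 Day 1. For the BSC-only group, and for subjects randomized but not treated, it uses a value dated no later than randomization.
- **Analysis.** Protocol Section 9.9.3 and SAP Section 2 leave the HRQoL methods to a separate plan, which is not among the documents.

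**The concern.** A patient-reported baseline in an open-label trial should be fixed before the subject can know the arm. The CCR option is chosen before randomization and the subject must be willing to receive it, so the allocation decides between AG-221 and one known alternative, which may be BSC only. The questionnaires ask about worry, tension, low mood, global health and anxiety. These are items that news of the allocation could move. The EQ-5D asks about the day itself; the past-week recall of the QLQ-C30 dilutes the effect for that instrument.

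If the baseline moves with the arm, a comparison based on change from baseline or adjusted for baseline inherits the movement, and the scheduled data contain no earlier score that would reveal it. ECOG status, rated by the clinician, is collected at screening and again on Day 1. The patient-reported measures have no such earlier value.

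A second issue follows from the SAP. A baseline window that closes at randomization for some groups and at first dose for others can make missing baseline data depend on the assigned group.

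**Working it through.** The plan gives no HRQoL figure to reproduce. The OS event calculation does not bear on this point. The check is a trace of the schedule and baseline rules, followed by the bias algebra.

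**1. Schedule.** HRQoL assessments scheduled before randomization (Table 3 and Section 6.1): 0. Interval from randomization to the first assessment (footnote d): 0 to 3 days. The fallback to screening results is empty for HRQoL, because none is collected there.

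**2. Which Day 1 form counts as baseline.** The form is assumed to be completed before dosing.

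| Group | Protocol 6.2.1 | SAP 5.1, form on the randomization date | SAP 5.1, form 1–3 days later |
|---|---|---|---|
| AG-221, azacitidine, LDAC or IDAC, treated | counts | counts | counts |
| BSC only | counts | counts | does not count |
| Randomized, not treated | no treatment start to anchor it | counts if completed | does not count |

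The two rules agree for treated subjects outside BSC only. They part for BSC-only subjects as soon as the form is dated after randomization. Among subjects whose pre-selected option was BSC only, a form completed 1–3 days after randomization would then be a baseline in the AG-221 arm but not in the CCR arm.

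**3. Bias if knowledge of the arm moves the baseline.** Define all differences as AG-221 minus CCR:

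- δ = true difference at follow-up without any effect of knowing the arm
- d = between-arm shift at baseline from knowing the arm
- p = the part of d still present at follow-up
- b = slope of follow-up on baseline score

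Randomization makes the expected baseline difference 0 apart from d, so:

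- Baseline difference: d
- Follow-up difference: δ + p
- Change-score contrast: δ + p − d, an error of size d − p, opposite in sign to d when d > p
- Baseline-adjusted contrast: about δ + p − b·d, an error of size b·d − p

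The documents give no d, p or b, so the values below are assumptions.

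If the effect has vanished by follow-up (p = 0), with b from 0.3 to 0.7:

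| d (points) | Change score: d | Adjusted: b·d |
|---|---|---|
| 2 | 2 | 0.6 to 1.4 |
| 5 | 5 | 1.5 to 3.5 |
| 10 | 10 | 3.0 to 7.0 |

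If part of it persists (d = 5, b = 0.5):

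| p | Change score: d − p | Adjusted: b·d − p |
|---|---|---|
| 0 | 5 | 2.5 |
| 2.5 | 2.5 | 0 |
| 5 | 0 | −2.5 |

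Subjects stay unblinded throughout, so p = 0 cannot be presumed. Over this range the change-score error runs from the full shift to nothing, and the adjusted error changes sign.

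**The case against.** **Knowledge of the arm is not shown.** Three days is a maximum. The IVRS entry on Day 1 in Table 3 is compatible with randomization that same day, and SAP Section 5.1 takes the randomization day as Day 1 for BSC-only subjects, although that is an analysis convention and not a visit rule. If randomization and Day 1 coincide, completion before staff contact could precede disclosure. This stands: a reader might infer that subjects already know their arm when they fill in the form, or that all 316 are affected, but no section says when they are told. What remains is that the plan allows the form to follow disclosure and does not record which came first.

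**The HRQoL plan has not been seen.** It may set its own baseline, population and model, so the BSC-only discrepancy is conditional on its adopting the SAP 5.1 rule. It cannot create a pre-randomization score.

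**Subjects never treated.** A reader might infer that a screening form would bring these subjects back into the comparison. It would not. Section 3.1.2 describes EOT evaluations for subjects with at least one dose, and Table 3 has no HRQoL entry in follow-up, so no later score is scheduled for them. Nor do the documents give a rate of non-starting or say that refusals are likelier in the CCR arm.

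**An earlier form is staler.** Screening can run 28 days, about 0.92 months (28 / 30.4375), or some 16% of the assumed 5.6-month CCR median survival (0.92 / 5.6). That is a fair objection to a form completed at any point in screening. It is met by placing the form shortly before the randomization call.

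**Conclusion.** The schedule facts are certain: no HRQoL score is planned before randomization, the first may come up to 3 days after it, and neither condition on completion protects against an arm already known. Influence on the baseline is therefore possible but not demonstrated.

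Its size and direction cannot be derived. A reader might infer that CCR subjects score worse on learning their arm and that an AG-221 benefit is thereby hidden. That requires a particular sign of d and an effect that has largely faded by follow-up, and the documents support neither. It also assumes an analysis of change from baseline or adjusted for baseline, which is left to the unseen plan.

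The mismatch between Protocol 6.2.1 and SAP 5.1 for BSC-only subjects is real as written. It matters only if the HRQoL plan follows SAP 5.1 and forms are completed after the randomization date.

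The consequence is confined to a secondary endpoint outside the OS/ORR/EFS testing sequence, so no alpha-controlled claim depends on it. The change is worth making because it is cheap and closes the route.

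**What to change.** **For any further enrollment.** In Table 3, Section 6.1 and Section 6.2.1, require both questionnaires to be completed before the IVRS randomization call and as close to it as practical, and make that score the HRQoL baseline. The cost is one tablet session of 15 to 20 minutes (10–15 for the QLQ-C30 plus about 5 for the EQ-5D, Section 6.9), moved rather than added. Some screen failures will complete it, and the score will be slightly older than a Day 1 score.

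**For subjects already enrolled.** The SAP was signed in June 2020, after the March 2019 interim analysis, so the schedule change may reach few subjects or none. The HRQoL plan should:

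- apply one baseline rule to all groups, reconciling SAP Section 5.1 with Protocol Section 6.2.1;
- state that the baseline may be post-randomization;
- report Day 1 scores and missingness by arm and by pre-selected CCR option.

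This needs only text and tables, with no new data collection.

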### 6.2.2. Unscheduled Visits

Should it become necessary to repeat an evaluation (eg, laboratory tests or ECG), the results of the repeat evaluations should be entered as appropriate in additional unscheduled visit pages of the eCRF.

[figure not shown]
### 6.2.3. End of Treatment

An EOT evaluation will be performed for subjects who are withdrawn from study treatment for any reason as soon as possible after the decision to permanently discontinue study treatment has been made. An administrative window of  $\pm 7$  days is permitted for the EOT visit, unless noted otherwise. If a subject is discontinued during a regularly-scheduled visit, all EOT evaluations should be completed at that visit.

The following evaluations will be performed as specified in the Table of Events, [Table 3](#). For each evaluation, the same parameters as required at screening or on Day 1 of Cycle 1 should be evaluated.

- Registration of treatment discontinuation in IVRS
- HRQoL (EORTC QLQ-C30 and EQ-ED-5L questionnaires)
- Treatment accountability (where applicable; refer to [Section 7.5](#))
- ECOG performance status
- Physical examination, vital signs and body weight. Significant findings are to be reported on the appropriate eCRF page.
- The following laboratory assessments will be done locally:
  - ECHO if clinically indicated
  - 12-lead ECG
  - A serum or urine (investigator's discretion under local regulations)  $\beta$ -hCG pregnancy test (sensitivity of at least 25 mIU/mL) (for FBCPs only)
- The following laboratory assessments will be done centrally:
  - Urinalysis and/or coagulation test if clinically indicated
  - Hematology panel
  - Chemistry panel

- Cardiac marker (not necessary for the EOT visit if it was last performed within 14 days unless clinically indicated)
- Fasting (preferred) lipid panel (not necessary for the EOT visit if it was last performed within 28 days unless clinically indicated)
- Evaluations of AEs, [REDACTED] concomitant medications, concomitant procedures and transfusions (monitored through 28 days after the last study treatment or until the EOT visit, whichever is longer)
- Bone marrow aspirate and/or biopsy, peripheral blood smear and, if applicable, cytogenetics, for response assessment (not necessary for the EOT visit if it was last performed within 28 days unless clinically indicated)
- Response to treatment and HI will be assessed if bone marrow samples are collected for assessing response at the EOT visit (see above)

### 6.3. Follow-up Phase

All subjects discontinued from study treatment for any reason other than withdrawal of consent for follow-up will continue to have the following assessments in the Follow-up Phase:

[figure not shown]
- AEs, [REDACTED] concomitant medications, concomitant procedures and transfusions for 28 days after the last study treatment or the EOT visit, whichever is longer.

Thereafter, SAEs made known to the investigator at any time that are suspected of being related to study treatment, as described in Section 10.1.

- Transfusions [REDACTED] will continue to be collected until the initiation of the first subsequent AML therapy after discontinuation from study treatment, death, lost to follow-up, withdrawal of consent for further data collection, or the End of Trial, whichever occurs first.
- Bone marrow aspirate and/or biopsy, peripheral blood smear and, if applicable, cytogenetics, available for both local and central review for assessing response or

disease status, every 12 weeks ( $\pm$  28 days) or more frequent if clinically indicated until PD, the initiation of the first subsequent AML therapy after discontinuation of study treatment, death, lost to follow-up, withdrawal of consent for further data collection, or the End of Trial, whichever occurs first.

- Response/disease status and HI will be assessed whenever bone marrow samples are collected for assessing response or disease status (see above)

- Survival follow-up every 4 weeks ( $\pm$  7 days) until death, lost to follow-up, withdrawal of consent for further data collection, or the End of Trial, whichever occurs first. Subsequent AML therapies should be collected at the same schedule as survival follow-up.
- Investigator-assessed response/ disease status to subsequent AML therapies will be collected. Specifically, the best response to a subsequent AML therapy and the first date achieving the best response, and progressive disease/relapse date during or after a respective subsequent AML therapy should be reported.
- Survival follow-up, subsequent AML therapies, and response/ disease status to subsequent AML therapies may be conducted by record review (including public records) and/or telephone contact with the subject, family, or the subject's treating physician.
- Females of childbearing potential should avoid becoming pregnant for 4 months after the last study treatment (6 months after the last dose of cytarabine), and male subjects and their partners should avoid conception for 4 months after the last study treatment (6 months after the last dose of cytarabine; 6 months after the last dose of azacitidine in Canada).

#### 6.4. Safety Assessment

Safety assessments include physical examination, vital signs, ECG, hematology, serum chemistry, cardiac markers, fasting (preferred) lipid panel, pregnancy testing (for FCBP subjects only), AEs, concomitant medications and procedures, and transfusions, will be performed at the frequency specified in [Table 3](#) or more frequently if clinically indicated. After screening, ECHO, urinalysis and coagulation will be performed if clinically indicated.

### **6.4.1. Adverse Events**

Refer to Section 10 for AE reporting. Information about common side effects already known about AG-221 and azacitidine can be found in the respective IBs or will be communicated between IB updates in the form of Investigator Notifications. Refer to United Kingdom (UK) Summary of Product Characteristics (SmPC) for information about common side effects already known about cytarabine. This information about common side effects will also be included in the subject ICF and should be discussed with the subject as needed during the study.

### **6.4.2. Urinalysis, Coagulation, Hematology, Serum Chemistry, Cardiac Markers and Fasting (Preferred) Lipid Panel**

All samples should be sent to the central laboratory. In the event that an immediate laboratory assessment is required to acutely manage a subject (eg, monitoring ALT increases of  $\geq 3$  x ULN; Appendix P), local laboratory tests may be used. In addition to collecting the local laboratory sample, a second sample should be collected and sent to the central laboratory.

Refer to Section 10.3 for information regarding abnormal laboratory values or whether test results constitute an AE.

## **6.5. Efficacy Assessment**

### **6.5.1. Disease Status or Response to Study Treatment**

Bone marrow aspirate (or biopsy if adequate aspirate is not attainable) samples will be collected for assessing disease status or response to study treatment at the frequency specified in Table 3 or more frequently if clinically indicated.

A bone marrow biopsy can be collected in conjunction with an aspirate if it is standard institutional practice or if clinical indicated (eg, evaluation of bone marrow cellularity). Whenever a bone marrow sample is collected, a peripheral blood smear is to be prepared.

In addition, whenever a bone marrow aspirate is obtained for confirming CR/CRi/CRp, morphologic relapse after CR/CRi/CRp or PD, a sample of the bone marrow aspirate is to be sent to the local or central cytogenetics laboratory (for sites without local analysis capability) for standard metaphase preparation and analysis of a minimum of 20 metaphase cells. A bone marrow biopsy can be used for cytogenetics testing if adequate aspirate is not attainable (note that specific handling of the biopsy is required for cytogenetics testing).

Bone marrow aspirate and/or biopsy, peripheral blood smear and cytogenetics collected throughout study must be available for both local and central review. A retrospective central review of all bone marrow aspirates and/or biopsies, peripheral blood smears and cytogenetics collected throughout study will be conducted by personnel blinded to subject treatment. The central cytogenetic review will provide standardized analysis and reporting for all subjects, regardless of the laboratory performing the initial analysis (local or central). The central assessments will be used in the statistical analyses. Disagreement between central and local assessments will be adjudicated by a third party reviewer and the adjudicated assessment will be used in the statistical analyses.

Response to study treatment will be assessed by the investigators and retrospectively by a blinded IRAC according to modified IWG AML response criteria (Appendix F) through

collection of central hematology parameters, central assessments of bone marrow aspirates and/or biopsies, peripheral blood smears and cytogenetics, and results of other pertinent tests.

Instructions for submission slides of bone marrow aspirate (and/or biopsy) and peripheral blood smear, and pertinent reports for central review are provided in the Study Reference and Study Central Laboratory Manuals.

[figure not shown]
In addition, investigator-assessed response/ disease status to subsequent AML therapies will be collected (see the details in Section 6.3).

